7.2. Participant Discontinuation/Withdrawal From the Study

In case a participant is withdrawn from the study intervention cohort for any of the reasons listed in Section 7.2 of the Master Protocol PLATFORMPAHPB2001, additional participants will not be entered.

7.2.1. Withdrawal From the Use of Research Samples

Refer to Section 7.2.1 of the Master Protocol PLATFORMPAHPB2001.

7.3. Lost to Follow-up

Refer to Section 7.3 of the Master Protocol PLATFORMPAHPB2001.

8. STUDY ASSESSMENTS AND PROCEDURES

Overview

Refer to Section 8 of the Master Protocol PLATFORMPAHPB2001.

The PRO assessments and ECGs should be completed before any tests, procedures or other consultations for that visit.

The total blood volume to be collected from each participant during planned assessments for the entire study will be approximately 1200 mL. In addition, PBMC samples (at selected sites only; approximately 300 mL), optional exploratory host genotyping and epigenetic research samples (approximately 60 mL) and optional intensive PK samples (approximately 66 mL) may be collected.

Note: The total blood volume to be collected from each participant may vary, depending on several factors (eg, unscheduled re-tests, re-sampling, individual variations).

Sample Collection and Handling

Refer to Section 8 of the Master Protocol PLATFORMPAHPB2001.

Study-specific Materials

In addition to the items described in Section 8 of the Master Protocol PLATFORMPAHPB2001, the investigator will be provided with the following supplies:

- A binder with the PRO instruments,
- Prescribing Information for ETV, TDF, and TAF,
- Contact information page(s).

8.1. Efficacy Assessments

All efficacy assessments will be performed at predefined time points as specified in the [Schedule of Activities](#).

Qualitative and quantitative HBsAg and HBeAg, and quantitative HBcrAg as well as anti-HBs and anti-hepatitis B e (HBe) antibodies will be determined using validated serologic assays in a central laboratory. Samples for the determination of HBsAg and HBeAg will be processed in real-time. Samples for the determination of HBcrAg can be analyzed in batch and at the sponsor's request.

HBV DNA and HBV RNA will be quantified at central laboratories using validated assays for the quantification of HBV DNA and HBV RNA. Samples for the determination of HBV DNA will be processed in real-time. Samples for the determination of HBV RNA can be analyzed in batch and at the sponsor's request.

HBeAg and anti-HBe antibody testing results from the Week 44 visit onwards will be provided for each participant to the investigator and the sponsor at the next visit (ie, from the Week 48 visit onwards). HBsAg and anti-HBs testing results from the Week 44 visit onwards will be provided for each participant to the investigator from FU Week 2 onwards. The blinded post-baseline results collected prior to the Week 44 visit will be provided to the investigator at the end of the study to complete the participant's medical records. Note that screening and Day 1 predose results are not blinded. HBV DNA results will be provided to the investigator and the sponsor from screening until the end of follow-up. In order to preserve the blinding during the study treatment phase, HBsAg, HBeAg, anti-HBs, and anti-HBe antibody tests cannot be done locally.

It is the responsibility of the investigator:

- To monitor HBV DNA results and ensure that JNJ-3989 and JNJ-6379 (or the matching placebos) are discontinued in participants with confirmed virologic breakthrough (see Section [7.1](#), Discontinuation of Study Intervention),
- To assess if NA treatment cannot be stopped at Week 48 due to any relevant change in participant baseline status with regards to ALT, HBV DNA levels and/or HBeAg status or any other event (see Section [6.6](#), Study Intervention Completion at Week 48),
- To assess whether restart of NA treatment during follow-up is needed (see Section [6.7](#), NA Re-treatment Criteria and Monitoring After Stopping of NA).

In participants enrolled at a site with an on-site Fibroscan device, Fibroscan assessments will be performed at different time points to determine changes in fibrosis levels.

Samples may be used by the sponsor for additional exploratory assessments analyzing the serologic and virologic characteristics of HBV infection and efficacy or safety of the study intervention.

8.1.1. Sequencing

Viral genome sequence analysis will be performed to evaluate mutations associated with the study intervention.

Sequencing of the HBV genome will be performed to monitor HBV variants present at the time points indicated in the [Schedule of Activities](#). The sequencing of samples may be triggered by the sponsor virologist based on changes in HBV DNA levels observed in each individual participant and the limits of the sequencing assay.

Samples may be used by the sponsor for additional assessments analyzing the serologic and virologic characteristics of the HBV infection and efficacy of the study intervention, including viral genotypic and phenotypic assessments.

8.1.2. Patient-reported Outcomes

The impact of HBV treatment on participants will be assessed using PROs at predefined time points (see [Schedule of Activities](#)). The following PRO instruments will be used: HBV-specific self-stigma scale and EQ-5D-5L questionnaire.

The PRO assessments will be performed by all participants. Participants should complete these assessments in their native language or if there is no version available in their native language, a version in a language in which the participant is fluent and literate. It is preferable that participants are able to read and write to complete the assessments by themselves. If a participant is unable to read or has visual or other physical limitations that make it difficult to read or complete the assessments, trained study-site personnel may read the questions and responses aloud exactly as they appear on the assessment and record the participant's responses.

Study-site personnel will record in the CRF whether the PRO assessments were performed during the study visit.

The participant should be provided a quiet place to complete the PRO assessments, and instructed how to complete the PRO assessments. When deciding which answer to report, participants should not receive any help from anyone accompanying them (such as family members and friends) or study-site personnel; the responses should reflect the participant's interpretation and response.

Participants' responses to the PRO questionnaires will not be reported as AEs or SAEs.

HBV-specific Self-stigma Scale, Version 1.0

The HBV-specific self-stigma scale is an HBV-specific PRO instrument designed to assess the experience and impact of self-stigma. The current version consists of 37 items. The items cover aspects of self-stigma such as a) devaluation, inferiority, and worthlessness, b) marginalization and alienation, c) secrecy and concealment, d) shame and guilt, and e) withdrawal and social isolation. Each of the 37 items is graded on a 5-point Likert scale (1 “Never”, 2 “Rarely”, 3 “Sometimes”, 4 “Often”, and 5 “Always”). It takes less than 15 minutes to complete the scale. The content validity of the scale is currently being evaluated and the data collected in this study will be used to assess the psychometric properties of the scale.^{33,39}

The HBV-specific self-stigma scale version 1.0 is provided in Section 10.10, Appendix 10, HBV-specific Self-stigma Scale.

5-Level EuroQol 5-Dimension Questionnaire

The EQ-5D-5L questionnaire is a brief, 2-page, generic health-related quality-of-life assessment that evaluates a subject’s self-rated health state on 5 dimensions (mobility, self-care, usual activities, pain/discomfort, anxiety/depression). Additionally, a VAS records the subject’s self-rated health on a vertical VAS where the endpoints are labelled ‘best imaginable health state’ (100) and ‘worst imaginable health state’ (0). This information can be used as a quantitative measure of health outcome as judged by the subject. EQ-5D scores include the following:

- EQ-5D Valuation Index score (a weighted scoring of the 5 dimension scores with a possible range from 0 to 1);
- EQ-5D VAS score (with a possible range from 0 [worst imaginable health] to 100 [best imaginable health]);
- EQ-5D descriptive system scores (5 scores reflecting each of the 5 dimensions ranging from 0 [no limitation] to 4 [incapacity]).

It takes about 2 minutes to complete the EQ-5D-5L questionnaire.

A representative example of the EQ-5D-5L questionnaire is provided in Section 10.11, Appendix 11, 5-Level EuroQol 5-Dimension Questionnaire (EQ-5D-5L).

8.2. Safety Assessments

Safety and tolerability (AEs, clinical safety laboratory assessments, ECGs, vital signs and physical examinations) will be evaluated as described in Section 8.2 of the Master Protocol PLATFORMPAHPB2001 and at predefined time points as specified in the [Schedule of Activities](#).

Additional clinical safety laboratory assessments specific for this protocol are described in Section 10.2, Appendix 2, Clinical Laboratory Tests.

8.2.1. Physical Examinations

Refer to Section 8.2.1 of the Master Protocol PLATFORMPAHPB2001.

8.2.2. Vital Signs

Refer to Section 8.2.2 of the Master Protocol PLATFORMPAHPB2001.

Clinically relevant abnormalities in vital signs are defined in Section [10.7](#), Appendix 7, Cardiovascular Safety Abnormalities.

8.2.3. Electrocardiograms

Refer to Section 8.2.3 of the Master Protocol PLATFORMPAHPB2001.

Clinically relevant abnormalities in ECG are defined in Section [10.7](#), Appendix 7, Cardiovascular Safety Abnormalities.

8.2.4. Clinical Safety Laboratory Assessments

Refer to Section 8.2.4 of the Master Protocol PLATFORMPAHPB2001.

In addition, urine samples for urine chemistry and renal biomarkers will be collected as noted in Section [10.2](#), Appendix 2, Clinical Laboratory Tests.

For this study, the laboratory abnormality of cholesterol increase is identified as laboratory abnormality of interest.

8.3. Adverse Events and Serious Adverse Events

Adverse events and SAEs will be evaluated as described in Section 8.3 of the Master Protocol PLATFORMPAHPB2001, including handling of pregnancy described in Section 8.3.5.

For further details on AEs and SAEs (Definitions and Classifications; Attribution Definitions; Severity Criteria; Special Reporting Situations; Procedures) as well as product quality complaints, refer to Attachment 4 of the Master Protocol PLATFORMPAHPB2001.

8.3.1. Time Period and Frequency for Collecting Adverse Event and Serious Adverse Event Information

Refer to Section 8.3.1 of the Master Protocol PLATFORMPAHPB2001.

8.3.2. Method of Detecting Adverse Events and Serious Adverse Events

Refer to Section 8.3.2 of the Master Protocol PLATFORMPAHPB2001.

8.3.3. Follow-up of Adverse Events and Serious Adverse Events

Refer to Section 8.3.3 of the Master Protocol PLATFORMPAHPB2001.

8.3.4. Regulatory Reporting Requirements for Serious Adverse Events

Refer to Section 8.3.4 of the Master Protocol PLATFORMPAHPB2001.

8.3.5. Pregnancy

Refer to Section 8.3.5 of the Master Protocol PLATFORMPAHPB2001.

8.3.6. Adverse Events of Special Interest

Events of Special Interest are significant AEs that are judged to be of special interest because of clinical importance, known class effects or based on nonclinical signals. Events of Special Interest that will be carefully monitored during the study include ISRs, ALT/AST elevations, renal complications, and events related to cholesterol increase (Section 8.2.4, Clinical Safety Laboratory Assessments). In addition, the following toxicities will also be carefully monitored: rash and acute systemic allergic reactions.

For participants reporting rash, ISRs, acute systemic allergic reactions, ALT/AST elevations, and renal complications as specified in the DAIDS Toxicity Grading Scale (see Section 10.9, Appendix 9, DAIDS Table), the following should be done.

8.3.6.1. Rash

Participants should be informed that they should contact their doctor immediately when they notice any generalized skin reaction. This skin reaction should be evaluated in the clinic the same day (if possible) or the next day.

All rash events should be captured in the AE section of the CRF. A separate Rash page will be completed in case of a rash event.

Monitoring of the evolution of rash events will be performed as described in Table 5 in Section 10.5, Appendix 5, Rash Management.

When safety blood samples are drawn as per the rash management guidelines, these should be processed by the local laboratory. The following parameters will need to be tested: AST, ALT, sedimentation rate, complete blood cell count (including hemoglobin, hematocrit, red blood cell [RBC] count, white blood cell [WBC] count, differential count [neutrophils, lymphocytes, monocytes, eosinophils, and basophils], and platelet count), and creatinine. The values of the local laboratory assessments need to be transcribed in the CRF by the study site personnel.

The participant may be treated symptomatically until the rash resolves. Oral antihistamines (eg, cetirizine, levocetirizine) and/or topical corticosteroids may provide symptomatic relief but effectiveness of these measures has not been established. If systemic corticosteroids exceeding 5 mg of prednisolone equivalent/day are required for treatment of rash, JNJ-3989 and JNJ-6379 (or placebos) need to be permanently discontinued. NAs can be continued. If the rash is considered to be most likely due to concomitant illness or non-study drugs, standard management, including discontinuation of the likely causative agent, should be undertaken.

8.3.6.1.1. Injection Site Reactions

At the time points specified in the [Schedule of Activities](#) or at an unscheduled visit if needed, an evaluation of the injection site will be performed based on participant's description and/or physical examination. Evaluation will include at a minimum the time of occurrence, time of resolution and a description of the abnormality including its maximal diameter. For each ISR, information on pain, erythema, induration and pruritus should be obtained as specified in the DAIDS scale (see Section 10.9, Appendix 9, DAIDS Table).

All ISRs (including ISRs below grade 1) will need to be recorded in the special events section of the CRF.

Digital pictures will be taken when considered appropriate; all efforts should be made to collect images in case of grade 3 and 4 ISRs. Digital pictures will only be taken and collected from participants who consent separately to this component of the study. If digital pictures are required, they should be de-identified and provided to the sponsor.

8.3.6.2. Acute Systemic Allergic Reactions

Grade 1 (Localized Urticaria [Wheals] With no Medical Intervention Indicated)

Participants may continue the intake of study interventions.

Cetirizine, levocetirizine, topical corticosteroids or antipruritic agents may be prescribed.

Participants should be advised to contact the investigator immediately if there is any worsening of the acute systemic allergic reaction.

Grade 2 (Localized Urticaria With Intervention Indicated, or Mild Angioedema With no Intervention Indicated)

Participants may continue the intake of study interventions.

Cetirizine, levocetirizine, topical corticosteroids or antipruritic agents may be prescribed.

Participants should be advised to contact the investigator immediately if there is any worsening of the acute systemic allergic reaction, in which case the participant will permanently discontinue the intake of JNJ-3989 and JNJ-6379 (or placebos). Rechallenge is not allowed. The participant's NA treatment may be discontinued based on investigator judgement in consultation with the sponsor.

Grade 3 (Generalized Urticaria, Angioedema With Intervention Indicated, or Symptoms of Mild Bronchospasm) and Grade 4 (Acute Anaphylaxis, Life-threatening Bronchospasm, or Laryngeal Edema)

Participants will permanently discontinue the intake of JNJ-3989 and JNJ-6379 (or placebos). Rechallenge is not allowed. The participant's NA treatment may be discontinued based on investigator judgement in consultation with the sponsor.

Participants will be treated as clinically appropriate. Participants should be followed until resolution of the AE and standard management should be undertaken.

8.3.6.3. Intervention-emergent ALT/AST Elevations

Elevated liver enzyme activity can be triggered by the underlying HBV disease as well as by the study intervention.

Management of intervention-emergent ALT/AST elevations is presented graphically in Section 10.6, Appendix 6, Intervention-emergent ALT/AST Elevations and is described below.

Any intervention-emergent elevation of ALT and/or AST $\geq 3x$ ULN and $\geq 3x$ nadir (ie, lowest value during study participation) should trigger an assessment of confounding factors (alcohol intake, change in concomitant medication, and comorbidities) and should trigger a confirmatory study visit to repeat laboratory testing of AFP, ALT, AST, ALP, bilirubin (total and direct), INR, albumin, and HBV DNA. Additional tests should be considered based on clinical judgement (Refer to 10.6, Appendix 6, Intervention-emergent ALT/AST Elevations). The confirmatory visit should be scheduled as soon as possible, preferably within 7 days of the receipt of the initial ALT/AST results. In case the repeat laboratory testing shows an isolated ALT/AST elevation (ie, with stable albumin, bilirubin [total and direct], and INR) the participant may continue study intervention. In case of confirmed ALT elevation $>1,000$ U/L and $\geq 3x$ baseline value, JNJ-3989 and JNJ-6379 (or their matching placebos) should be discontinued. In both cases, NA treatment should be continued. The participant will be monitored (laboratory testing of ALT, AST, ALP, bilirubin [total and direct], INR, albumin, and HBV DNA) on a weekly basis until ALT and/or AST levels have returned to $<5x$ ULN and HBV DNA is $<20,000$ IU/mL.

If the ALT and/or AST level is $\geq 3x$ ULN and $\geq 3x$ nadir and is associated with any of the following laboratory results or clinical symptoms:

- INR ≥ 1.5 , OR
- direct bilirubin $>1.5x$ ULN, OR
- serum albumin <3.0 g/dL, OR
- ascites, hepatic encephalopathy, or liver-related symptoms (eg, severe fatigue, nausea, vomiting, right upper quadrant pain in the absence of an alternative medical explanation), OR
- other indication of reduced liver function

the participant should discontinue JNJ-3989 and JNJ-6379 (or their matching placebos) and should be monitored on a weekly basis or as per good clinical practice until ALT and/or AST levels have returned to <5x ULN and HBV DNA is <20,000 IU/mL and, if present, liver-related symptoms have improved. NA treatment should be continued. Additional tests can be considered based on clinical judgement.

The NA re-treatment criteria and monitoring after stopping of NA are presented in Section [6.7](#).

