1.3.1. Schedule of Activities – Screening and Study Intervention Phase

Phase	Screening	Double-blind Study Intervention ^a													
		W0 ^d	W2	W4	W8	W12	W16	W20	W24	W28	W32	W36	W40	W44	W48/WD ^b
Study Week (W)	W 4 to 0 ^c														
Study Day (Window)	28	1	15 (+/ 2d)	29 (+/ 2d)	57 (+/ 2d)	85 (+/ 2d)	113 (+/ 3d)	141 (+/ 3d)	169 (+/ 3d)	197 (+/ 3d)	225 (+/ 3d)	253 (+/ 3d)	281 (+/ 3d)	309 (+/ 3d)	337 (+/ 3d)
Screening/Administrative															
ICF ^e	X														
ICF for optional pharmacogenomic samples	X														
Inclusion/exclusion criteria ^f	X														
Prestudy therapy (including prior anti HBV therapy)	X														
Medical/surgical history and demographics ^g	X														
Preplanned surgery/procedure(s)	X														
Fibroscan or liver biopsy ^h	X														
Abdominal ultrasound ⁱ	X														
Serum IgM anti HBc antibody test	X														
Study Intervention															
Randomization to intervention arm within this ISA		X													
Administer JNJ 3989 (or placebo)		X		X	X	X	X	X	X	X	X	X	X	X	
Intake of JNJ 6379 (or placebo) and NA ^j		X	X	X	X	X	X	X	X	X	X	X	X	X	X
Dispense JNJ 6379 (or placebo) and NA		X		X	X	X	X	X	X	X	X	X	X	X	(X) ^k
Oral study intervention accountability			X	X	X	X	X	X	X	X	X	X	X	X	X
Safety Assessments															
Complete physical examination ^l	X									X					X
Symptom directed physical examination, including body weight		X	X	X	X	X	X	X		X	X	X	X	X	
Vital signs ^m	X	X	X	X	X	X	X	X	X	X	X	X	X	X	X
Triple 12 lead ECG ⁿ	X	X		X		X			X			X			X
Injection site reactions		X	X	X	X	X	X	X	X	X	X	X	X	X	X
Liver ultrasound ^o			X						X						X

Phase	Screening	Double-blind Study Intervention ^a													
		Study Week (W)	W 4 to 0 ^c	W0 ^d	W2	W4	W8	W12	W16	W20	W24	W28	W32	W36	W40
Study Day (Window)	28	1	15 (+/- 2d)	29 (+/- 2d)	57 (+/- 2d)	85 (+/- 2d)	113 (+/- 3d)	141 (+/- 3d)	169 (+/- 3d)	197 (+/- 3d)	225 (+/- 3d)	253 (+/- 3d)	281 (+/- 3d)	309 (+/- 3d)	337 (+/- 3d)
Clinical Laboratory Tests															
Hematology	X	X	X	X	X	X	X	X	X	X	X	X	X	X	X
Blood chemistry (including liver function tests) ^{p,q,r}	X	X	X	X	X	X	X	X	X	X	X	X	X	X	X
Blood coagulation	X	X		X	X	X	X	X	X	X	X	X	X	X	X
Urinalysis ^s	X	X		X	X	X	X	X	X	X	X	X	X	X	X
Urine chemistry ^t	X	X		X	X	X	X	X	X	X	X	X	X	X	X
Renal biomarkers ^u		X				X				X			X		X
Testing for hepatitis A, B, C, D, and E virus, HIV 1 and 2 ^r	X														
FSH test (postmenopausal women only) ^v	X														
Alpha fetoprotein ^r	X									X					X

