- a. All follow-up study visits are to be scheduled relative to the last dose of JNJ-3989/JNJ-6379/placebo. An unscheduled visit can be performed upon the investigator's discretion, in case of HBV DNA elevations, ALT elevations, other signs of worsening of liver disease, or for any other reason during follow-up.
- b. Participants who withdraw consent during follow-up will be offered an optional safety follow-up visit to occur on the day of consent withdrawal. For the optional safety follow-up visit, assessments are at the investigator's discretion and could be similar to the early WD visit.
- c. No JNJ-3989/JNJ-6379/placebo will be administered or dispensed during follow-up. Administration/Dispensation of NA is only applicable for participants who could not stop NA treatment at Week 48, or for those who met the NA re-treatment criteria. In between study visits, participants will take NA at home and they will bring their NA treatment with them to each study visit. At study visits, the NA treatment should be taken on site.
- d. Vital signs include supine SBP, DBP, pulse rate, and body temperature.
- e. All ECGs will be read centrally.
- f. A liver ultrasound is recommended every 6 months for HCC screening in high-risk populations (ie, participants with a family history of HCC, Asian males >40 years, Asian females >50 years; Africans and African Americans).
- g. Biochemistry samples must be taken after fasting for at least 10 hours for measurement of phosphate, calcium, creatinine, and lipids.
- h. Creatinine clearance (eGFR calculated by the CKD-EPI formula) will be assessed.
- i. ALT/AST elevations (ie, ALT and/or AST ≥ 3 ULN and ≥ 3 nadir [ie, lowest value during study participation]), should trigger an assessment of confounding factors (alcohol intake, change in concomitant medication, and comorbidities) and a confirmatory visit, to be scheduled preferably within 7 days of the receipt of the initial ALT/AST results, to repeat laboratory testing of AFP, ALT, AST, ALP, bilirubin (total and direct), INR albumin, and HBV DNA. Additional tests should be considered based on clinical judgement. For more details and further management guidance, refer to Section 8.3.6.3, Intervention-emergent ALT/AST Elevations and Section 10.6, Appendix 6, Intervention-emergent ALT/AST Elevations.
- j. Liver function tests only.

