- v. The investigator should consider to re-start NA treatment per local standard of care at the EOS visit (Follow-up Week 48) for participants who discontinued NA treatment at Week 48, who did not re-start NA treatment during the follow-up phase, and who did not achieve and maintain HBsAg seroclearance. NA will not be provided by the sponsor after the final study visit.
- w. NA treatment should be re-started in accordance with the NA re-treatment criteria (see Section [6.7](#), NA Re-treatment Criteria and Monitoring After Stopping of NA and Section [10.13](#), Appendix 13, for guidance after stopping NA treatment.

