Week 48), and weekly visits for patients with ALT/AST ≥ 3 x upper limit of normal (ULN) and ≥ 3 x nadir (ie, lowest value during study participation) until stabilization.

Increases in ALT and HBV DNA are frequently seen in patients after discontinuation of NA treatment. These ALT elevations can be reflecting an activation of the host cellular immune response and can as such lead to functional cure. Cases of fulminant HBV reactivation with fatal outcome were described after cessation of NA treatment, but the vast majority of such cases were described in patients with decompensated liver disease at the time of NA discontinuation. These patients are not eligible to participate in the study. Still, a vigilant follow-up of patients during this phase of the study is critical to ensure patient safety. Signs of decreased liver function or an HBV DNA value of $>100,000$ IU/mL (irrespective of confirmation and/or ALT increase) will trigger immediate re-initiation of NA treatment based on protocol-defined NA re-treatment criteria (see Section 6.7, NA Re-treatment Criteria and Monitoring After Stopping of NA).

Re-initiation of NA treatment is also required in case of confirmed HBeAg seroreversion (HBeAg positive after it was negative at NA completion), in case of confirmed* ALT increase (>5 x ULN) in combination with increased HBV DNA replication ($>2,000$ IU/mL), and in case of confirmed* increased HBV DNA replication at higher levels ($>20,000$ IU/mL).

*At least 4 weeks apart

A post-treatment HBV DNA value of $>20,000$ IU/mL should trigger re-testing of ALT/AST, HBV DNA, and total and direct bilirubin within a maximum of 7 days from receipt of the data and further repeats as necessary (ie, weekly until HBV DNA returns to $<20,000$ IU/mL). A post-treatment HBV DNA value of $>2,000$ IU/mL (but $<20,000$ IU/mL) should trigger a re-test within 14 days from receipt of the data and further repeats as necessary (ie, every other week until HBV DNA returns to $<2,000$ IU/mL). A post-treatment ALT value of >5 x ULN should trigger re-testing of ALT, AST, ALP, total and direct bilirubin, INR, albumin, and HBV DNA on a weekly basis until ALT and AST levels have returned to <5 x ULN. Additional re-testing and/or earlier restarting of NA treatment is at the investigator's discretion, even if the above cut-offs are not yet met.

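### Protocol 8.3.6.3 opens ALT/AST monitoring at 3x ULN but closes it below 5x ULN, so the stop rule can be met on entry, even with abnormal liver function; in follow-up Section 4.2 says otherwise

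*Protocol*

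**What the plan says.** Protocol 8.3.6.3 starts when ALT and/or AST are at least 3x ULN and at least 3x nadir. That prompts a check for confounders and a confirmatory visit, preferably within 7 days. There are then two branches.

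- **Isolated elevation.** Dosing may continue unless ALT is confirmed above 1,000 U/L and at least 3x baseline. In either case a liver panel and HBV DNA are repeated "on a weekly basis until ALT and/or AST levels have returned to" below 5x ULN, with HBV DNA below 20,000 IU/mL.
- **Reduced liver function or symptoms.** The same enzyme entry applies, plus INR of 1.5 or more, direct bilirubin above 1.5x ULN, albumin below 3.0 g/dL, liver-related symptoms, or another sign of reduced function. JNJ-3989 and JNJ-6379 stop and NA continues. The participant "should be monitored on a weekly basis or as per good clinical practice until ALT and/or AST levels have returned to" the same two limits, with improvement of liver-related symptoms if there are any.

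For follow-up, Section 4.2 describes "weekly visits for patients with ALT/AST" at or above 3x ULN and 3x nadir. The sentence ends "lowest value during study participation) until stabilization". That last word is not defined for ALT/AST, although 8.3.6.5 defines it for hematology. Later in 4.2 a post-treatment ALT above 5x ULN "should trigger re-testing of ALT, AST, ALP, total and direct bilirubin, INR, albumin, and HBV DNA on a weekly basis", which is also the rule in 6.7 and Appendix 13.

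In the follow-up Schedule of Activities (1.3.2), footnote i covers elevations at 3x ULN and 3x nadir and says: "For more details and further management guidance, refer to Section 8.3.6.3, Intervention-emergent ALT/AST Elevations". Footnote w points to 6.7 and Appendix 13 "for guidance after stopping NA treatment".

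**The concern.** A monitoring rule should not be complete at the moment it starts. Here the exit limit lies above the entry limit, so part of the group that 8.3.6.3 places under weekly tests has no weekly tests required.

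The second branch matters more. INR, direct bilirubin or albumin brings the participant in, yet none of them appears in the exit rule.

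In follow-up, a site that follows 4.2 and a site that follows 8.3.6.3 can both be compliant and test the same participant at different intervals. The protocol has already tightened post-treatment monitoring after a case of subacute hepatic failure (2.3.3), so timing in this group deserves one clear rule.

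**Working it through.** No sample size or power figure is involved. The check is threshold logic, with ALT or AST written as *a* and nadir as *n* (both in multiples of ULN) and HBV DNA as *D*.

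**1. Where entry and exit overlap (8.3.6.3)**

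- Entry: a ≥ 3 and a ≥ 3n, that is a ≥ max(3, 3n).
- Exit: a < 5 and D < 20,000 IU/mL.
- Both at once, if D < 20,000: max(3, 3n) ≤ a < 5.

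| Nadir (x ULN) | Entry at | Band where exit is met on entry |
|---|---|---|
| 1.0 or less | 3.0 | 3.0 to <5 |
| 1.5 | 3 × 1.5 = 4.5 | 4.5 to <5 |
| 5/3 (about 1.67) or more | 5.0 or more | none |

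Inclusion criterion M03/A02 requires screening ALT below 2.0x ULN, so the ALT nadir is below 2.0x ULN. The ALT band is therefore empty only for nadirs from about 1.67x to below 2.0x. If D is 20,000 IU/mL or more, exit is not met on entry.

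**2. Reduced-liver-function branch, worked example**

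Take ALT 4x ULN, nadir 0.5x ULN, HBV DNA 1,000 IU/mL, INR 1.6 and no symptoms.

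- Entry: 4 ≥ 3; 4 ≥ 3 × 0.5 = 1.5; INR 1.6 ≥ 1.5. Met.
- Exit: 4 < 5; 1,000 < 20,000; no symptoms to improve. Met at the same visit, with INR still 1.6.

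If symptoms are present, exit is not met on entry, because they must also improve.

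**3. Follow-up sections side by side**

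| Section | Weekly tests or visits start | They end |
|---|---|---|
| 8.3.6.3 (via 1.3.2 footnote i) | after entry at 3x ULN and 3x nadir | ALT and/or AST <5x ULN, HBV DNA <20,000 |
| 4.2, first statement | 3x ULN and 3x nadir | stabilization, undefined |
| 4.2 later; 6.7; Appendix 13 | ALT >5x ULN | ALT and AST <5x ULN |

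In the 3x to <5x band with HBV DNA below 20,000 IU/mL, 6.7 and Appendix 13 do not conflict with 8.3.6.3. The first statement in 4.2 is the one that differs. The and/or in the 8.3.6.3 exit also leaves open whether one enzyme below 5x is enough; 6.7 requires both.

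**4. Required liver tests off NA, per 28 days after the confirmatory visit**

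- Under 4.2: 28/7 = 4, assuming stabilization is not reached within 28 days.
- Under 8.3.6.3 and the 4-weekly schedule: 28/28 = 1. If footnote i triggers a new confirmatory visit at each routine draw, 1 + 1 = 2.
- Longest routine chemistry gap with ±4-day windows, without such a repeat: 28 + 4 + 4 = 36 days.

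The 14-day HBV DNA re-test in 6.7 is not counted, because the text does not say that it includes ALT.

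**5. Comparison with the SAP**

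SAP 5.3.1.1.6 starts a biochemical flare from the same 3x/3x criterion, once confirmed, and ends it at a 50% fall from peak and below 3x ULN. At 4x ULN a participant can still be in a flare by the SAP while 8.3.6.3 allows weekly tests to end.

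**The case against.** The strongest reply is a two-tier reading: 3x ULN prompts the confirmatory visit, and weekly tests are meant for values that have exceeded 5x, since the text speaks of levels having returned below it. Section 4.2 is a rationale section, its later paragraph uses 5x, and the operational sections agree on the 5x and 20,000 limits. The Appendix 6 flowchart is not reproduced in the available text and could settle the band either way. This has weight, but 8.3.6.3 states no 5x floor for weekly tests, and 4.2 attaches weekly visits expressly to 3x. Nor does the two-tier reading supply the missing laboratory recovery condition.

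Several stronger inferences are tempting and should not be drawn.

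- **That these participants are left without cover.** They are not. The confirmatory visit remains and may recur at each routine draw under footnote i. Off NA, chemistry is due about every 4 weeks. Section 8.3.6.3 allows extra tests on clinical judgement, 6.7 requires immediate NA restart when liver function is falling, and the IDMC and flare panel review ALT flares.
- **That abnormal INR, bilirubin or albumin may simply be dropped.** Section 2.3.3 requires clinically significant abnormalities persisting at early discontinuation to be followed to resolution or agreed stabilization. It sets no frequency, so it does not fill the gap in the 8.3.6.3 exit rule.
- **That INR goes untested for 84 days in follow-up.** The coagulation row, as extracted, suggests gaps from follow-up Week 12 to 24 and 24 to 36. The same table prints another row inconsistently (its third visit falls at Week 32 in one copy and Week 36 in the other), and footnote i can bring INR forward. The figure should not be relied on.
- **That weekly testing is mandatory in the reduced-function branch.** That branch already allows good clinical practice as the alternative, so intervals may differ between sites by design.
- **That such participants move straight to 12-weekly visits.** Section 1.3.2 requires stable HBV DNA and ALT first. The term is undefined, but calling a fresh rise to 3x nadir stable would be strained.

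**Conclusion.** The point holds as a mismatch between entry and exit rules and a conflict between sections, read literally. It covers participants from 3x ULN (or 3x nadir, if higher) to below 5x ULN with HBV DNA below 20,000 IU/mL, and it vanishes at a nadir of about 1.67x ULN or more. The most important part is the reduced-liver-function branch, where the laboratory abnormality that opens monitoring is absent from the rule that closes it.

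Off NA, the size is up to 4 required liver tests per 28 days under 4.2 against 1 or 2 under 8.3.6.3 and the routine schedule. The consequence is later recognition of worsening. The documents do not say how many participants to expect in the band, and the conclusion assumes that Appendix 6 adds no rule for it. A reader might infer some effect on the trial's results; the documents give no reason to expect a change in the primary analysis, the power or the SAP flare incidence. The case for acting is safety at low cost.

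**What to change.** 1. **8.3.6.3, reduced-liver-function branch.** End monitoring only when ALT and AST are both <5x ULN, HBV DNA is <20,000 IU/mL, any symptoms have improved, INR is <1.5 (or back to baseline for participants on anticoagulants), direct bilirubin is ≤1.5x ULN and albumin is ≥3.0 g/dL.
2. **8.3.6.3, isolated-elevation branch.** Replace and/or with and in the exit rule. For participants who entered at 3x to <5x ULN, continue weekly tests until HBV DNA is <20,000 IU/mL and ALT and AST are either both <3x ULN, or both <5x ULN with no further increase over two consecutive visits. The 5x and 20,000 limits stay, so the rule is nowhere looser than now.
3. **4.2.** Replace the undefined stabilization end point with a cross-reference to this rule, and check that the Appendix 6 chart matches.
4. **1.3.2.** Do not allow the 12-weekly schedule until the applicable 8.3.6.3 exit rule has been met. Do not make that rule the general definition of stable: its <3x ULN arm has no trend condition, so a rise from 0.5x to 2.9x ULN would qualify.

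The cost is protocol wording and a few extra weekly laboratory visits.
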